### **End of Study Assessment**

Verify completion of day 5 study questionnaires: VAS, Brief Pain Inventory, GAD-7, BAApress Questionnaire and Pain Management Satisfaction

### **Primary Outcomes**

Patient reported pain and general activity scores (Visual Analogue Scale) and (Brief Pain Inventory)

### **Secondary Outcomes to be measured:**

- Pain medication usage. Trajectory of am and pm pain scores
- General Anxiety Disorder Scale (GAD-7). Patients are asked to rate the frequency of anxiety symptoms daily on a Likert scale (0-3). In general, patients with GAD or other common anxiety disorders exhibit GAD-7 scores of 10 or greater.
- Pain Management Satisfaction to determine patient satisfaction
- Acupressure Acceptability questions - We will ask acceptability questions. "How satisfied were you with how your pain has been treated?" using the Likert scale to measure "Very satisfied =5, Satisfied=4, Somewhat satisfied = 3, Somewhat dissatisfied= 2, Dissatisfied 1, Very Dissatisfied 0." Would you consider using auricular acupressure in the future for pain or if recommended by your nurse or physician? a. No, would not use again (Score of 0) b. Maybe (Score of 1), c. Yes, I would consider using in the future (Score of 2) 3. Is there anything else you would like to tell us that may be helpful for us to know regarding ear acupressure? (Each answer will be collected and assessed for future studies).
- BAA Press placement survey (interventionists only): The Interventionist (Acupressure nurse) will be asked to capture time related to completion of study tasks and other qualitative questions to assess overall feasibility.
- Additional Data collection: contact information, relevant demographic data that will be recorded are: DOB, age, gender, ethnicity/race. Relevant medical history will be duration of pain medications including narcotic use (in years) and comorbid chronic or acute pain diagnoses.

Study activity	Baseline a	Day 1	Day 2	Day 3/End of study
Informed Consent signed	x			
Data Collection Form	x	x	x	x
Complete Baapress Questionnaire	x	x	x	x
Administer or record Pain score assessment (VAS) b	x	x	x	x
Brief Pain Inventory	x	x	x	x
Pain Management Satisfaction				x
Generalized Anxiety Disorder Scale (GAD-7)	x	x	x	x
Acupressure placement and patient education		x		
*Optional interventionist recording of AA placement d		x		
Study team collect completed questionnaire				x
Compensation administration				x
BAA press placement survey (interventionist only)	x	x	x	x

a Baseline and Day 1 can be completed on the same day. Baseline activities are to be completed prior to Acupressure administration.

b The study team will perform the pain score assessment with the participant two times a day for three days.

c Participants will receive reminders to complete the study questionnaires if discharged prior to 3 days.

d Only participants who agree to participate in the optional recording/photography at the time of informed consent will have their acupressure placement session recorded.

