### **Objectives**

1. To determine psychiatric patients' acceptance of BAApress as an adjunct treatment to address co-occurring pain.
2. To determine if the addition of BAApress protocol will lower pain scores and decrease pain medication usage.
3. To determine ability of ED nurses to incorporate BAApress into their workflow.

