that moderate pressure is being applied. Description of sensations felt by participant will be recorded by the BAApress interventionist.

- The BAApress interventionist will document pad placement and activation in EPIC.
- BAApress interventionist will review with participant how and when to activate each pad and give participant a picture of a right and left ear with the acupressure points location on each ear. Participants will be reminded to gently press on each pad for 30 seconds at least three times a day to activate for a total of 3 days.
- If the acupressure pads fall off before day 3, they will not be replaced. The BAApress interventionist will record the missing pad/pads.
- After completion of day 3 study activities, the study team will remove the acupressure pads by gently pulling on the edges of the pad and lifting off with their fingers or using tweezers to loosen the pad if needed.
- If participants are discharged prior to 3 days, they will be contacted via telephone call by study personnel and/or via text messaging depending on participant preference to remind them to complete the questionnaire and to activate their pads 3 times per day.
- At the end of the third day, the study personnel will call the patient, or they will receive a text letting them know the study team needs to arrange a telephone call to provide instruction on how to remove the acupressure pads. If participant cannot be reached by phone, they will be instructed on removing pads by gently pulling on the edges of the pad and lifting off with their fingers or using tweezers to loosen the pad if needed. Participants will be reminded to complete final post intervention questionnaires after removal of pads that study personnel will review with them.
- The BAApress interventionist nurse may record and take pictures of the treatment visit. These recordings will be used to ascertain fidelity to the intervention protocol as it relates to a) proper placement of acupressure seeds and b) provision of instructions to the participant.
- Each study participant will be asked to sign a separate consent giving permission for the intervention to be recorded and used for education and research purposes. The recordings will be done to limit exposure of the study participant's face.

- The study team will perform Visual Analogue Scale (VAS) and Brief Pain Inventory with participants one to two times a day for 3 days.

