- The study team will have the participant complete GAD-7 every morning for 3 days.
- The study team will complete BAApress Questionnaire daily with participant every morning for 3 days.

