### **Analytical Plan**

Sample Size: This is a feasibility study with no control group. Target enrollment is 10- 20 participants. Data from this study will be used to generate parameter estimates to calculate power for future studies.

Results will be analyzed initially using descriptive statistics. Any group comparisons will be done using chi square tests for proportions, and t-tests or ANOVA procedures for continuous variables.

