### **Compensation**

Participants completing the study will receive \$25.00 in a Walmart gift card.

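### The plan has no step that asks the acceptability questions when a participant withdraws, and no denominator, so those most likely to reject BAApress may leave no answer on Objective 1

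*Combined protocol and SAP*

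**What the plan says.** The first item under Objectives reads "To determine psychiatric patients' acceptance of BAApress as an adjunct treatment to address co-occurring pain". The patient-reported measures closest to it are in Secondary Outcomes to be measured. One entry there is "Pain Management Satisfaction to determine patient satisfaction". The next, on acceptability, holds a satisfaction rating scored 0 to 5, a free-text comment, and "Would you consider using auricular acupressure in the future for pain or if recommended by your nurse or physician", scored 0 (No), 1 (Maybe) or 2 (Yes).

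On timing:

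- The activity table marks Pain Management Satisfaction in one column only, Day 3/End of study.
- The End of Study Assessment section lists the same form among day 5 questionnaires. The two passages disagree.
- The acceptability items have no row of their own in the table, and the text does not name the form that carries them.
- A separate patient form is given daily: "The study team will complete BAApress Questionnaire daily with participant every morning for 3 days". The table also marks it at baseline. Its items are in an appendix that is not reproduced.
- In the Day 1 section, the bullet on contact at the end of the third day adds: "Participants will be reminded to complete final post intervention questionnaires after removal of pads that study personnel will review with them".

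On losses, the Day 1 section covers pads that come off by themselves (recorded, not replaced) and early discharge (contact by telephone or text). A footnote to the activity table repeats the reminders after early discharge. No section describes an assessment at withdrawal, a question on why someone stopped, or what happens when a participant chooses to take the pads off. The Analytical Plan promises descriptive statistics and states no analysis set, denominator or missing-data rule.

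**The concern.** A participant who withdraws because they dislike the pads is direct evidence on acceptance. As written, the plan has no point at which that person's view is collected, because the one scheduled satisfaction form falls at the end. Early discharge and telephone or text follow-up make some loss of contact realistic in this setting. With no stated denominator, the natural summary is a percentage of returned forms, and that percentage can look better than acceptance among everyone treated.

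This is the first objective of a feasibility study, and the Analytical Plan says its data will supply parameter estimates for later trials. With "Target enrollment is 10- 20 participants", each missing person is 1/20 = 5% to 1/10 = 10% of the sample.

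**Working it through.** **Nothing to reproduce.** The plan gives no dropout rate, acceptance rate or acceptability threshold, and the target of 10-20 is not derived from any. All rates below are assumptions for illustration. Acceptance means answering Yes to the future-use question.

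**Size of the bias.** Let m be the share with no answer, p_r the Yes rate among responders, and p_m the Yes rate the missing would have given. The true rate is (1 − m)·p_r + m·p_m, so a responders-only figure is off by

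bias = p_r − [(1 − m)·p_r + m·p_m] = m·(p_r − p_m).

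With p_r = 80%:

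| m | p_m = 20% | p_m = 40% | p_m = 80% | p_m = 90% |
|---|---|---|---|---|
| 10% | +6 points | +4 | 0 | −1 |
| 20% | +12 | +8 | 0 | −2 |
| 30% | +18 | +12 | 0 | −3 |

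For example, 0.20 × (0.80 − 0.40) = 0.08 and 0.20 × (0.80 − 0.20) = 0.12.

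**What the reported figure could look like**, with exact (Clopper-Pearson) 95% intervals:

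- 20 participants with pads placed, 4 without an answer, 13 of 16 responders say Yes. Responders only: 13/16 = 81.3% (54.4 to 96.0). All 20, missing counted as No: 13/20 = 65.0% (40.8 to 84.6). Missing counted as Yes: (13 + 4)/20 = 85.0%.
- 10 participants, 2 without an answer, 6 of 8 say Yes. Responders only: 6/8 = 75.0% (34.9 to 96.8). Missing counted as No: 6/10 = 60.0% (26.2 to 87.8). Missing counted as Yes: (6 + 2)/10 = 80.0%.

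In both examples the two bounds are 20 points apart (85.0 − 65.0 and 80.0 − 60.0), which is the share missing.

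**Compared with sampling error.** With no one missing, 8/10 has an exact interval of about 44% to 98%, and 16/20 about 56% to 94%. The biases in the table are smaller than the half-widths of these intervals. The interval, however, describes chance variation around the responders' rate and does not correct a shift caused by who answers.

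**The case against.** A reader might infer that anyone who takes the pads off never answers, that Objective 1 is measured in completers only, and that the result is biased upward. The documents do not support that reading.

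- **Pads off is not out of the study.** Nothing says that losing or removing pads ends participation. The daily assessments carry no condition on pad status, and patients discharged early are contacted and reminded. Someone who removes pads and stays in follow-up is still due the final form. The gap is withdrawal and loss to contact.
- **The future-use item may not be end-only.** Its form and time are not given, and the daily BAApress Questionnaire could carry it. That form's baseline mark suggests otherwise but is weak evidence: the same table marks the interventionists' placement survey on days when no pads are placed.
- **No completers-only analysis is stated.** The denominator is unspecified, and responders-only is merely the likely default.
- **The direction is assumed.** If contact is lost for reasons unrelated to the pads, the bias is near zero. If the missing were more favourable than responders, it would be slightly negative.
- **The gift card proves little.** "Participants completing the study will receive" it, but completing is not defined as keeping the pads on. Finishing the questionnaires is an equally natural reading.
- **The link to Objective 1 is an inference.** The plan does not say which items answer it, acceptability is a secondary outcome, and the satisfaction item asks about pain treatment in general.

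These points stand, and they narrow the concern. They do not supply an assessment at withdrawal, a reason-for-stopping item, or a rule for missing answers.

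**Conclusion.** The concern holds in a limited form. The satisfaction form is scheduled once, at the end, with Day 3 and day 5 in conflict. The future-use item has no stated form or time. No step collects either item, or a reason, from a participant who withdraws or is about to be lost to contact. Those most likely to reject BAApress may therefore be absent from the data on Objective 1, and a summary of returned forms could overstate acceptance.

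Under the assumed rates (80% Yes among responders, 20-40% among the missing), the overstatement is 8-12 points at 20% missing, with 4-6 at 10% and 12-18 at 30%. It vanishes if the missing would answer alike. Upward bias is plausible, not demonstrated. The change is worth making because it is cheap and affects both what is collected and what can be concluded.

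**What to change.** 1. Name the form that carries the acceptability items and when it is given. Reconcile the activity table (Day 3) with the End of Study Assessment section (day 5).
2. In both places, make Pain Management Satisfaction and the acceptability items due at the end of study, at withdrawal or at early pad removal, whichever comes first and with the participant's agreement. Add one item on the reason for stopping.
3. In the Analytical Plan, report acceptability over all participants who had pads placed. Give the number missing and the missing=No and missing=Yes bounds beside the responders-only figure. Showing both bounds is preferable to counting every non-answer as non-acceptance in the main figure, which could bias the result downward. The bounds also cover people lost before any form can be given.

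The cost is a short amendment, one existing form given earlier to a few participants, and one extra item. The acceptability figure may turn out lower or be shown with a wider range.

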### **Analytical Plan**

Sample Size: This is a feasibility study with no control group. Target enrollment is 10- 20 participants. Data from this study will be used to generate parameter estimates to calculate power for future studies.

Results will be analyzed initially using descriptive statistics. Any group comparisons will be done using chi square tests for proportions, and t-tests or ANOVA procedures for continuous variables.

### **Human Subjects Protection**

Good Clinical Practices and HIPAA guidelines will be followed to ensure the safety and wellbeing of patients electing to participate in this study. PHI used during this study will be collected and recorded in accordance with the standards set forth in the Health Insurance Portability and Accountability Act (HIPAA). Confidentiality of medical information will be maintained throughout the study. All paper case report forms (CRFs) and informed consent forms (ICFs) will be stored in a locked drawer. Study participants will be assigned a unique identifier that will be used on CRFs. Data collected for this COVID-19 ALS Registry will also be stored and analyzed electronically in Atrium Health's REDCap Database. REDCap is a secure web platform for building and managing online database projects and surveys and is used extensively by academic and research institutions. This REDCap study will further restrict access to study staff.

### **Subject Recruitment Methods**

To assist with recruitment. Patients when admitted to Atrium Behavioral Health Emergency Room may be identified by screening behavioral health treatment team and referred to study personnel.

Study personnel will review eligibility and approach patient regarding participation. Only eligible patients willing to complete all survey's pre and post procedures and provide written consent will participate. The study team will ensure that the participant understands the voluntary nature of participating in the research study and that study participation study will not affect the care that they will receive.

The study personnel will maintain a record of eligible study participants. This list will include name, MRN, psychiatric and pain diagnosis, and will be kept in a secure file on a secure computer and only accessible to study staff. The file of eligible participants will be destroyed at the end of recruitment.

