As of January 1, 2018, The Joint Commission requires hospitals to have non-pharmacologic modalities available for pain management in an effort to decrease the need for opioids. Acupuncture and acupressure have been used for centuries in the management of a variety of disorders including pain. A recent meta-analysis (Zhong et al., 2019) of 26 RCTs (all included studies were in China) favored the use of acupressure for pain management over usual care based on total effective rate (RR =1.25, [CI= 1.13, 1.37], p <.0001) and total analgesia use (RR=0.41, [CI= 0.24, 0.68] p = .0006). There were no serious adverse events reported in the 26 trials (N=1063 in treatment groups) and no withdrawals from the studies were reported due to adverse events. More recently, in an effort to increase access to non-pharmacological modalities for pain management, the VA has developed a **battlefield auricular acupressure (BAApress) protocol**. Unlike acupuncture, acupressure can be easily applied with training and is within the scope of practice for nurses, according to the North Carolina Board of Nursing (NCBON, 2013). Although acupressure has been used for centuries in traditional Chinese medicine, there are few studies assessing the use of nurse-initiated acupressure as an adjuvant for co-occurring pain. Thus, we propose assessing the effectiveness of BAApress for chronic and acute pain management for psychiatric patients in a psychiatric emergency room setting. In addition, by analyzing measures and demographics we hope identify patients that may benefit most from BAApress acupressure.

This feasibility study is being performed in collaboration with the BAApress training and Intervention Fidelity study IRB00084011. This study is similar to Fidelity study IRB00068022, Auricular Acupressure for Pain Management as a Non-Opioid Adjuvant Therapy for Opioid Tolerant Patients (PI [name]). The purpose of this study is to test the feasibility of Emergency Department nurse-initiated battlefield auricular acupressure as an adjunct to medication for pain management for psychiatric Emergency Department Observation patients.

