### **Confidentiality and Privacy**

Confidentiality will be protected by collecting only information needed to assess study outcomes, minimizing to the fullest extent possible the collection of any information that could directly identify subjects, and maintaining all study information in a secure manner. To help ensure subject privacy and confidentiality, only a unique study identifier will appear on the stored data collection forms. Any collected patient identifying information corresponding to the unique study identifier will be maintained on a linkage file, stored separately from the data. The linkage file will be kept secure, with access limited to designated study personnel.

Following data collection, subject identifying information will be destroyed three years after the completion of the study consistent with data validation and study design, producing an anonymous analytical data set. Data access will be limited to study staff. Data and records will be kept locked and secured with any computer data password protected. No reference to any individual participant will appear in reports, presentations, or publications that may arise from the study.

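### Acceptability is measured only among patients who joined, and no count of patients approached or declining is planned, so uptake among those approached is not set to be captured

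*Combined protocol and SAP*

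**What the plan says.** All references are to the combined protocol and SAP.

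- **Purpose and objective.** Background, Rationale and Context states: "The purpose of this study is to test the feasibility of Emergency Department nurse-initiated battlefield auricular acupressure". Objectives, item 1, is to determine psychiatric patients' "acceptance of BAApress as an adjunct treatment to address co-occurring pain".
- **Route into the study.** The care team identifies and refers candidates (Interventions and Interactions; Subject Recruitment Methods). Then: "Study personnel will review eligibility and approach patient regarding participation". Entry is restricted: "Only eligible patients willing to complete all survey's pre and post procedures and provide written consent will participate".
- **Acceptability measures.** Secondary Outcomes lists a satisfaction rating, a scored future-use item ("Would you consider using auricular acupressure in the future for pain") and an open question on ear acupressure. A daily BAApress Questionnaire is also completed with participants; its content is in an appendix that is not in the supplied text.
- **The eligibility record.** Subject Recruitment Methods says of it: "This list will include name, MRN, psychiatric and pain diagnosis". Its fate is also given: "The file of eligible participants will be destroyed at the end of recruitment".
- **Enrolled participants' identifiers.** Confidentiality and Privacy places these elsewhere: "Any collected patient identifying information corresponding to the unique study identifier will be maintained on a linkage file, stored separately from the data".
- **Analysis.** The Analytical Plan sets a target of 10 to 20 participants and begins with descriptive statistics. Neither it nor the outcome sections name an uptake, consent or refusal figure.

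**The concern.** Acceptance is asked only of people who had already said yes to the study and to all its surveys. A finding that most of 20 participants would use ear acupressure again reads the same whether nearly all or only a minority of the patients approached agreed to join. For a feasibility study in this population, that difference matters to how the result is read. It also matters to whoever plans the next study and needs to know how many patients to approach per enrolment.

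The timing makes the gap worth raising now. If approaches and refusals are not counted as they happen, and the only eligibility record is then destroyed, the denominator cannot be rebuilt.

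**Working it through.** **Is the denominator captured anywhere?** The plan has no uptake figure to reproduce, so the first step is to follow the recruitment path and see what is counted.

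1. Referral by the care team: described, no count planned.
2. Eligibility review: a list is kept with name, record number and diagnoses.
3. Approach: described, no count planned, and no such field named on the list.
4. Consent or refusal: no field named on the list, and no refusal count or reason planned.
5. Study activities: the schedule starts at signed consent. The Data Collection Form's content is not shown, but it is scheduled for participants from baseline, so it would not be expected to cover decliners.

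**What could the list supply?** Its wording allows two readings.

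- *It covers all eligible patients.* The separate linkage file for enrolled participants makes this plausible. The number eligible could then be counted before destruction, but not the number approached or declining.
- *It covers enrolled participants only.* It then never held the denominator.

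On either reading, following the text as written leaves uptake among those approached uncaptured.

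**What would a tally yield?** Inputs: enrolled = 10 or 20 (Analytical Plan). Uptake of 70%, 50% and 30% is assumed, because the documents give none. Approached = enrolled / uptake, rounded to a whole number. The interval is exact (Clopper-Pearson) 95%: for x of n, the lower limit is the 2.5% point of Beta(x, n − x + 1) and the upper limit is the 97.5% point of Beta(x + 1, n − x).

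| Enrolled | Assumed uptake | Approached | Estimate | 95% CI |
|---|---|---|---|---|
| 10 | 70% | 10/0.7 = 14.3, so 14 | 10/14 = 71% | 42-92% |
| 10 | 50% | 10/0.5 = 20 | 10/20 = 50% | 27-73% |
| 10 | 30% | 10/0.3 = 33.3, so 33 | 10/33 = 30% | 16-49% |
| 20 | 70% | 20/0.7 = 28.6, so 29 | 20/29 = 69% | 49-85% |
| 20 | 50% | 20/0.5 = 40 | 20/40 = 50% | 34-66% |
| 20 | 30% | 20/0.3 = 66.7, so 67 | 20/67 = 30% | 19-42% |

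With 20 enrolled, the intervals for about 70% and about 30% uptake do not overlap (49-85% against 19-42%). With 10 enrolled they do (42-92% against 16-49%).

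**The case against.** The strongest reply is that the acceptance objective concerns the treatment, and the plan measures that directly through the future-use item, the satisfaction rating, the open question and the daily questionnaire. This stands. A reader might infer that the objective goes unmeasured or fails; the documents do not support that. Uptake shows willingness to join a study, and a patient may refuse because of the surveys or acute illness. It is context for the participant figure and does not correct it.

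A second reply is that the gap is inferred from silence. Nothing forbids staff from counting the list before it is destroyed, and destruction is a privacy safeguard for an identifiable file. This also stands in part. A reader might infer that reporting uptake is ruled out, or that staff will certainly keep no tally; the text says neither. If the list covers all eligible patients, the number eligible could be counted, and because the same staff review eligibility and approach patients, it would be a reasonable but imperfect proxy. It would still not separate patients who were never approached from those who refused, and no section plans even that count.

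A third reply is that descriptive statistics would cover recruitment counts as a matter of routine. They can summarise only what was recorded.

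Finally, uptake would describe only patients whom the care team had already selected as suitable, and at 10 enrolled it would be imprecise. Both points are correct. They limit how the figure should be labelled and read.

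**Conclusion.** The point holds as a limit on the feasibility conclusion. As written, the study can report acceptability among its 10 to 20 participants, but uptake among patients approached is not planned to be captured and could not be recovered once recruitment closes. No primary outcome, secondary outcome or planned analysis becomes wrong or biased as a description of participants.

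On the assumed uptake values, a tally at 20 enrolled could tell high uptake (about 70%) from low (about 30%); at 10 enrolled it would give only a rough figure. The conclusion assumes that the appendices not in the supplied text hold no log of approaches or refusals, and that staff do only what the protocol describes. Severity is minor: this is a cheap improvement.

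**What to change.** 1. In Subject Recruitment Methods, state whether the list of eligible patients includes those who decline.
2. Keep an anonymous running tally of patients eligible, approached, consented and declined, with any reason a patient volunteers. Retain the de-identified totals before the file is destroyed; destruction of the identifiable file can stay as planned.
3. Add one line to the Analytical Plan: uptake = consented / (eligible and approached), with an exact 95% confidence interval. Label it as willingness to join the study among patients referred by the care team, and report it separately from acceptability among participants.

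**Cost.** A few tally entries and one or two protocol sentences, with no new patient procedure. Adding columns to the existing list instead would place refusal status beside the identifiers of people who did not consent, so that route needs IRB agreement; the anonymous tally avoids it. The estimate would be rough at 10 enrolled, and the headline may look less favourable once uptake is shown beside it.
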